- Enrollment to last visit during LTT: $100 * (\text{total number of data days from the IWRS enrollment date to the last visit date during LTT}) / (\text{Last visit date during LTT} - \text{IWRS enrollment date} + 1)$. Last visit date during LTT is same as EOT visit date, but derived for all treated subjects (see Section 5.3).

eDiary compliance will be summarized as a continuous parameter and as the number and percentage of subjects in the following categories: $\geq 90\%$ compliance; $\geq 80\%$ compliance. Subject sources are the evening report, PoM, and SM. The site source is the medication reconciliation form.

Drug Accountability Compliance

Drug accountability compliance will be summarized by enrollment group and overall with the number and percentage of enrolled subjects in the following categories:

- At least one kit dispensed
- Did not return at least one kit dispensed and discontinued the study
- Did not return any kit dispensed and discontinued the study.

Kit dispensed and kit returned will be identified from “yes” responses to the questions “was this kit dispensed” and “was this kit returned”, respectively.

4.8.2 Adverse Events

Refer to the BHV3000 Core SAP for AE start date imputation, AE counting rules, definition of treatment-emergent adverse events (TEAEs), and definition of AEs related to study drug.

Tables will present the number and percentage of subjects experiencing AEs by SOC and PT, unless specified otherwise.

A by-subject listing of all AEs will be provided for screened subjects that will flag on-treatment and treatment-emergent AEs. Additional by-subject listings of deaths, SAEs, AEs leading to study drug discontinuation, hepatic-related AEs, and AEs of special interest (i.e., potential drug abuse, CV, and suicidality) will be provided for screened subjects. Refer to the BHV3000 Core SAP for listing content and AEs of special interest.

AE Overview

An AE overview without SOC and PT will present the number and percentage of subjects with any the following AEs: any AE; severe AE; AE related to study drug (unlikely related, possibly related, or related); SAE; SAE related to study drug; AE leading to study drug discontinuation; AE leading to death; hepatic-related AE; severe hepatic-related AE; hepatic-related SAE; hepatic-related AE leading to study drug discontinuation; potential drug abuse AE; CV AE; suicidality AE. An AE overview will be produced for each the following analysis periods and populations:

- Pre-treatment AEs for screened subjects by enrollment group and overall
- Pre-treatment AEs for treated subjects by enrollment group and overall
- TEAEs for treated subjects by enrollment group and overall
- On-treatment AEs for treated subjects by enrollment group and overall
- On-treatment AEs for treated subjects by subgroup level and overall for all subgroups of interest specified in Section 4.2.6
- Follow-up AEs for follow-up subjects by enrollment group and overall.

Pre-Treatment AEs

Pre-treatment AEs will be summarized by SOC and PT by enrollment group and overall for screened subjects for the following endpoints:

- AEs
- SAEs.

Pre-treatment AEs will be summarized by SOC and PT for treated subjects by enrollment group and overall for the following endpoints:

- AEs by severity (total, mild, moderate, severe, moderate or severe, not reported)
- SAEs.

On-Treatment AEs

On-treatment AEs will be summarized by SOC and PT for treated subjects by enrollment group and overall for the following endpoints:

- AEs by severity*
- TEAEs by severity
- TEAEs occurring in $\geq 2\%$ of subjects in any enrollment group after rounding. Percentages will be displayed rounded to integers, and AEs will be displayed in alphabetical order by SOC and PT.
- AEs occurring in $\geq 2\%$ of subjects in any enrollment group or subgroup level[^]
- AEs occurring in $\geq 5\%$ of subjects in any enrollment group by severity (primary safety endpoint, see Section 4.6.1)
- AEs occurring in $\geq 10\%$ of subjects in any enrollment group
- Exposure-adjusted AEs
- AEs related to study drug by severity*
- AEs related to study drug occurring in $\geq 2\%$ of subjects in any enrollment group or subgroup level[^]
- SAEs (primary safety endpoint, see Section 4.6.1)*
- Exposure-adjusted SAEs
- AEs leading to study drug discontinuation (primary safety endpoint, see Section 4.6.1)*
- Hepatic-related AEs by severity (secondary safety endpoint, see Section 4.6.2)[#]
- Hepatic-related SAEs[#]
- Hepatic-related AEs leading to study drug discontinuation (secondary safety endpoint, see Section 4.6.2)[#]
- Additional AEs of special interest: potential drug abuse[^]; CV; suicidality. Potential drug abuse AEs will be displayed in alphabetical order by severity and PT without SOC.

Endpoints marked with “*” will also be summarized by subgroup level and overall for all subgroups of interest specified in Section 4.2.6. Endpoints marked with “#” will also be summarized by subgroup level and overall only for extrinsic exposure factors (see Section 4.2.6). Endpoints marked with “^” will also be summarized by subgroup level and overall only for key extrinsic exposure factors (see Section 4.2.6).

Refer to the BHV3000 Core SAP for exposure-adjusted AEs. Calculations for on-treatment exposure-adjusted AEs will set reference start date to the study drug first dose date, reference end date to the study drug end dose date, and reference last date to the study drug last dose date + 7 days.

Follow-up AEs

Follow-up AEs will be summarized by SOC and PT for follow-up subjects by enrollment group and overall for the following endpoints:

- AEs by severity
- SAEs.

AEs in All Safety Analysis Periods Combined

AEs in all safety analysis periods combined (i.e., pre-treatment, on-treatment, and follow-up) will be summarized by SOC and PT for treated subjects by enrollment group and overall for the following endpoints:

- AEs leading to study drug discontinuation (primary safety endpoint, see Section 4.6.1)
- Hepatic-related AEs leading to study drug discontinuation (secondary safety endpoint, see Section 4.6.2).

4.8.3 **Laboratory Tests**

Clinical safety laboratory testing will be performed at early termination and the following visits: Screening; Baseline; Weeks 4, 24, and 52 for the 52-week PRN (2-8) and (9-14) dosing groups; Weeks 4 and 12 for the 12-week EOD+PRN and PRN (2-8) dosing groups. Urinalysis will be collected at early termination and the following visits: Baseline; Week 52 for the 52-week PRN (2-8) and (9-14) dosing groups; Week 12 for the 12-week EOD+PRN and PRN (2-8) dosing groups. Lipids (cholesterol, HDL cholesterol, LDL cholesterol, triglycerides) will be collected at early termination and the following visits: Baseline; Weeks 24 and 52 for the 52-week PRN (2-8) and (9-14) dosing groups; Week 12 for the 12-week EOD+PRN and PRN (2-8) dosing groups. LFTs (ALT, AST, ALP, TBL, direct bilirubin) will be collected routinely at Screening, Baseline, all visits during the treatment period, early termination, and Follow-up Week 2 for all enrollment groups.

Clinically significant laboratory abnormalities will be identified as grade 3 to 4 laboratory test results. Refer to the BHV3000 Core SAP for laboratory tests of clinical interest and toxicity grading. Laboratory test groups of clinical interest will include hematology, serum chemistry, and urinalysis.

LDL cholesterol and triglycerides will be analyzed as separate laboratory test parameters according to 8-hour fasting status: fasting \geq 8 hours; not fasting \geq 8 hours; overall. Refer to the BHV3000 Core SAP for additional details.

Tables, listings, and figures (TLFs) will be provided to show data in both Systeme Internationale (SI) and United States (US) unit systems, if applicable.

Tables will present results by treatment group and overall, and laboratory tests alphabetically within laboratory test group, as applicable. In analyses of the worst abnormality or category in a safety analysis period, subjects must have a non-missing measurement in the safety analysis

period to be included for a given parameter. In shift from baseline analyses, subjects must have a non-missing measurement at baseline and in the safety analysis period to be included for a given parameter.

By-subject listings of the following select laboratory test groups will be provided for screened subjects: hematology; serum chemistry; urinalysis (US units only); pregnancy (US units only); endocrinology, serology, drug screen, and miscellaneous laboratory tests (US units only). In addition, a by-subject listing of LFT values and ratios to ULN (i.e., ALT, AST, TBL and ALP) will also be provided for screened subjects. Refer to the BHV3000 Core SAP for listing content.

Worst Laboratory Test Abnormalities

A primary safety endpoint is the frequency of clinically significant laboratory test abnormalities (see Section 4.6.1). The number and percentage of treated subjects with the worst (highest) on-treatment laboratory test abnormality will be presented in the following toxicity grade categories for each graded laboratory test: Grade 0; Grade 1 to 2; Grade 3 to 4; Grade 3; Grade 4. Grade 3 to 4 abnormalities are considered clinically significant. Bi-directional tests will be assessed separately for each component (i.e., calcium low, calcium high).

The worst on-treatment laboratory test abnormalities will also be summarized by subgroup level and overall for treated subjects for all subgroups of interest described in Section 4.2.6.

The worst follow-up laboratory test abnormalities will also be summarized by enrollment group and overall for follow-up subjects.

Laboratory Test Low/Normal/High Shifts From Baseline

Laboratory test low/normal/high shifts from baseline to any on-treatment abnormal value will be summarized by treatment group and overall as the number and percentage of treated subjects in each category (low, normal, high), which does not depend on US or SI units. Subjects with both low and high on-treatment values will be counted in both on-treatment low and high categories (thus, these categories are not mutually exclusive). Subjects must have only normal values on treatment to be counted in the on-treatment normal category.

LFT ULN Shifts From Baseline

LFT ULN shifts from baseline to the worst (highest) on-treatment value will be summarized by treatment group and overall as the number and percentage of treated subjects in the following categories: \leq ULN, $>$ ULN to $\leq 3 \times$ ULN, $> 3 \times$ ULN to $\leq 5 \times$ ULN, $> 5 \times$ ULN to $\leq 10 \times$ ULN, $> 10 \times$ ULN to $\leq 20 \times$ ULN, and $> 20 \times$ ULN (US and SI units are identical). LFTs will be limited to ALT and AST.

Laboratory Test Toxicity Grade Shifts From Baseline

Laboratory test toxicity grade shifts from baseline to the worst (highest) on-treatment toxicity grade will be summarized by treatment group and overall as the number and percentage of treated subjects in each toxicity grade category (Grade 0, Grade 1, Grade 2, Grade 3, Grade 4) for each graded laboratory test. Bidirectional tests will be assessed separately for each component (e.g., calcium, low; calcium, high).

Laboratory Test Changes From Baseline Over Time

Values and changes from baseline in hematology and serum chemistry laboratory tests will be summarized using descriptive statistics at baseline and each scheduled visit in the on-treatment and follow-up safety analysis periods.

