If in the 2-8 or 9-14 moderate to severe migraines/month group, patients will be instructed to take study medication at the onset of a migraine (of mild to severe intensity), with a maximum of one tablet per day. If in the 4-14 moderate to severe migraines/month group, patients will be instructed to take study medication every other calendar day, regardless of whether the patient has a migraine. However, they may take a tablet at the onset of a migraine (of mild to severe intensity), even if the migraine begins on a day they are not scheduled to dose.

Patients are required to record migraine occurrence and severity and all study medication doses in the eDiary and standard of care migraine treatment taken in the paper diary. Patients will also use the eDiary to complete the PoM and SM.

Study visits will be roughly every 2 weeks during the first month and then every 4 weeks until Week 52 (or Week 12 for patients in the EOD+PRN dosing group).

Patients will return to the study site at the end of Week 52 (or Week 12 for patients in the EOD+PRN dosing group) for the End of Treatment (EOT) Visit. There is also a Follow-Up Visit 14 days after the Week 12/Week 52/EOT Visit.

Protocol Version 5.0 was amended to Version 6.0 to re-open study enrollment in the 2-8 moderate to severe migraine attacks per month group to approximately 20 subjects at select sites in order to assess safety of rimegepant in combination with FDA-approved calcitonin gene-related peptide (CGRP) antagonist biologics (Aimovig™, Ajovy™, Emgality™). Patients at select sites with a history of 2-8 moderate to severe migraines/month taking a stable FDA-approved CGRP antagonist biologic will be instructed to take a maximum of one tablet per calendar day for 12 weeks to treat migraines of mild, moderate, or severe intensity. These subjects will follow the same study visit schedule as subjects in the 12-week EOD+PRN dosing group.

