2.3.1 Primary Estimands

The estimands corresponding to the primary endpoint for this study are shown in [Table 1](#).

Table 1: Estimands for the Primary Objective

Objective	Safety and Tolerability
Population	All treated subjects
Variables	Number and percentage of subjects with AEs occurring in $\geq 5\%$ of treated subjects by severity, SAEs, AEs leading to study drug discontinuation on treatment, and clinically significant laboratory abnormalities on treatment
Pop. Summary	Frequency by enrollment group and overall

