4.6.1 Primary Safety Endpoints

The following primary endpoints to examine safety and tolerability are summarized by enrollment group and overall: frequency and severity of AEs occurring in $\geq 5\%$ of treated subjects, SAEs, AEs leading to study drug discontinuation, and clinically significant laboratory abnormalities.

On-treatment AEs as described above will be shown in separate tables by SOC and PT for each endpoint (AEs occurring in $\geq 5\%$ of subjects in any enrollment group by severity [mild, moderate, severe, moderate or severe, not reported, total], SAEs, AEs leading to study drug discontinuation). The 5% cut applies to the percentage of subjects with a PT in any enrollment group, regardless of severity. See Section 4.8.2 for additional details about AEs, and a comprehensive list of AE tables. Refer to the BHV3000 Core SAP for rounding rules.

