Exposure-adjusted on-treatment cumulative LFT elevations will also be summarized for treated subjects with the number and percentage of subjects with LFT elevations, along with patient-years and exposure-adjusted rates based on exposure up to time of first LFT elevation (see Section 4.8.2).

By-subject longitudinal LFT plots will display all normalized results (i.e., LFT ratio of value to ULN) regardless of study period for AST, ALT, ALP and TBL on the y-axis versus study week of laboratory result on the x-axis for treated subjects with any of the following LFT elevations during a safety analysis period (pre-treatment, on-treatment, follow-up): ALT $> 3 \times$ ULN; AST $> 3 \times$ ULN; TBL $> 2 \times$ ULN; ALP $> 2 \times$ ULN. Study week is defined as study day/7 (see Section 5.5). Each figure will also display treated migraine onsets, start of the on-treatment safety analysis period, and start of the follow-up safety analysis period.

Additionally, an evaluation of Drug-Induced Serious Hepatotoxicity (eDISH) scatter plot will display the maximum TBL ratio of value to ULN on the y-axis versus the maximum ALT ratio of value to ULN on the x-axis, where the maxima will be in the same safety analysis period but not necessarily concurrent. Both axes will be on the \log_{10} scale. Ratios $< 0.1 \times$ ULN will be set to 0.1. Sample sizes in the legend will represent subjects with paired ratios. A horizontal reference line will be placed at $2 \times$ ULN, and a vertical reference line will be placed at $3 \times$ ULN. The lower left quadrant will be labeled “Normal Range”, the upper left quadrant will be labeled “Hyperbilirubinemia”, the lower right quadrant will be labeled “Temple’s Corollary”, and the upper right quadrant will be labeled “Possible Hy’s Law Range.” The following eDISH scatter plots will be produced for treated subjects: (1) on-treatment by enrollment group; (2) on-treatment by average rimegepant exposure; (3) on-treatment by average rimegepant exposure for the EOD+PRN dosing group; (4) on-treatment by enrollment group for treated subjects who

took ≥ 14 tablets per 4 weeks for ≥ 12 weeks; (5) by safety analysis period (pre-treatment, on-treatment, follow-up) across enrollment groups pooled; (6) on-treatment by enrollment group for treated subjects who took ≥ 20 tablets per 4 weeks for ≥ 4 weeks; (7) on-treatment by enrollment group for treated subjects with near-daily dosing.

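### AEs leading to study drug discontinuation, a primary endpoint, are given only as crude percentages, although EOD+PRN is treated for up to 12 weeks and nearly all as-needed patients for up to 52

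*SAP*

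**What the plan says.** SAP 4.6.1 counts among the primary safety endpoints "SAEs, AEs leading to study drug discontinuation, and clinically significant laboratory abnormalities". The population summary in SAP 2.3.1 is "Frequency by enrollment group and overall".

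The entry "AEs leading to study drug discontinuation (primary safety endpoint, see Section 4.6.1" appears twice in SAP 4.8.2: once for the on-treatment period and once for all safety periods combined. The default format there is: "Tables will present the number and percentage of subjects experiencing AEs by SOC and PT, unless specified otherwise". The on-treatment entry also carries the mark that extends it to all subgroups of interest.

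Exposure adjustment is planned elsewhere. SAP 4.8.2 lists it for on-treatment AEs and, separately, as "Exposure-adjusted SAEs", and it fixes the reference dates for the calculation. SAP 4.6.3.1 adds: "Exposure-adjusted on-treatment cumulative LFT elevations will also be summarized for treated subjects". No such entry exists for AEs leading to discontinuation. The omission is not just a matter of abbreviated text, because SAP 4.6.1 says: "See Section 4.8.2 for additional details about AEs, and a comprehensive list of AE tables".

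On treatment length, SAP 2.1 has visits "every 4 weeks until Week 52 (or Week 12 for patients in the EOD+PRN dosing group", and Protocol 7.2.2 limits dosing to 12 and 52 weeks accordingly. The exception is about 20 patients on a CGRP biologic, who are treated for 12 weeks but counted in PRN (2-8) (SAP 2.1 and 4.2.1).

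**The concern.** A crude percentage is a risk over whatever time each patient was treated. Here that time differs between columns by design, because treatment length is fixed by the enrollment group. The problem is therefore not one of subgroups formed by achieved exposure. A patient in a 52-week column has about four times as long in which to stop for an AE as a patient in the EOD+PRN column. The figure in the overall column has no single time horizon.

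Tolerability is part of the primary objective, and EOD+PRN is the regimen with scheduled dosing. A reader who looks across the columns could credit that regimen with better tolerability when only the time at risk differs.

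Two other planned outputs might seem to cover this, but they do not:

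- The Kaplan-Meier tables in SAP 4.8.1 show time to stopping rimegepant for any reason. They count everyone with a recorded completion status as discontinued, so completers are events, and the EOD+PRN curve falls near Week 12 by design.
- The subgroup tables are still crude percentages, and time on rimegepant and cumulative tablets are themselves cut short by the event.

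**Working it through.** **The plan's own figures.** The only numeric planning figures are the zero-event bounds in SAP 4.1, and they reproduce. For N = 2000, 1 − 0.05^(1/2000) = 0.001497 (stated 0.0015). For N = 800, 1 − 0.05^(1/800) = 0.003738 (stated 0.00375). They say nothing about how often or when patients stop for AEs, so every rate below is an assumption.

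**Inputs from the documents.** Dosing up to 12 or 52 weeks (Protocol 7.2.2); about 1200, 600 and 200 patients in PRN (2-8), PRN (9-14) and EOD+PRN (Protocol synopsis and Section 5); about 20 twelve-week patients within PRN (2-8) (SAP 2.1); on-treatment window to last dose + 7 days (SAP 5.4).

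**Constant equal weekly hazard, full retention.** If p is the 52-week risk, the 12-week risk is 1 − (1 − p)^(12/52).

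| Assumed 52-week risk | 12-week risk | Ratio |
|---|---|---|
| 2% | 0.47% | 4.30 |
| 3% | 0.70% | 4.28 |
| 5% | 1.18% | 4.25 |
| 10% | 2.40% | 4.16 |

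The low-rate limit is 52/12 = 4.33. Adding the 7-day window to both gives 53/13 = 4.08. If 20 of 1200 PRN (2-8) patients are treated for 12 weeks, then at 3% that column shows (1180 × 3.00 + 20 × 0.70)/1200 = 2.96%, and the ratio is 4.23.

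**Other-cause dropout.** With AE hazard λ and other-cause hazard μ, the crude risk to time t is λ/(λ+μ) × [1 − exp(−(λ+μ)t)]. The table takes the 3% case.

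| Other-cause dropout by Week 52 | 12 weeks | 52 weeks | Ratio |
|---|---|---|---|
| 20% | 0.68% | 2.69% | 3.94 |
| 40% | 0.66% | 2.35% | 3.56 |
| 60% | 0.63% | 1.97% | 3.12 |

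**Hazard not constant.** If a share s of the 52-week risk falls in weeks 1-12, the ratio is 1/s: 2.5 for 40%, 2.0 for 50%, 1.3 for 75% and 1 for 100%. A hazard that rises with time would exceed 4.33. For example, a Weibull shape of 1.3 gives (52/12)^1.3 = 6.7 in the low-rate limit. So 4.3 is the ceiling for constant or declining hazards only.

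**Per tablet instead of per week.** EOD+PRN means 42 to 84 tablets in 12 weeks. One tablet per historical attack (assumption) gives 2 × 12 = 24 to 8 × 12 = 96 a year in PRN (2-8), and 9 × 12 = 108 to 14 × 12 = 168 in PRN (9-14). The tablet ratio to EOD+PRN is then 24/84 = 0.29 to 96/42 = 2.29 for the first group and 108/84 = 1.29 to 168/42 = 4.0 for the second.

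**After the fix.** At a constant hazard and 3% 52-week risk, λ = −ln(0.97)/52 per week. With 52.18 weeks per year, this is 3.06 per 100 patient-years in every column. Cumulative incidence through Week 12 is 0.70% in every column. The crude display would show 0.70% against 3.00%.

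**Precision.** The same assumption gives 200 × 0.0070 = 1.4 expected events in EOD+PRN, with probability (1 − 0.0070)^200, about 25%, of none.

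**The case against.** The study is single-arm and descriptive. No objective compares regimens, no between-group test is planned, and the percentage by enrollment group is the stated estimand and matches the protocol endpoint. That is right, so the SAP cannot be said to draw a biased comparison. It sets up a display from which a reader may draw one.

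The missing rate can nearly be recovered. SAP 4.8.1 reports total patient-years by enrollment group, and the event counts come by the same groups. Because the event ends dosing, count divided by patient-years is close to the adjusted rate, although AE onset may precede the last dose. Time on rimegepant is also shown by group. This stands: the defect is one of presentation, and no information is lost. It does not remove the case for putting a primary endpoint on a common time base when AEs and SAEs already are.

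The effect on the overall column is small. With 5% in 1800 patients and 1.18% in 200, it reads (1800 × 5 + 200 × 1.18)/2000 = 4.6% instead of 5%. This also stands, so the group columns matter more.

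A reader might infer that the every-other-day regimen will look four times better tolerated. The documents do not support that. It needs a constant weekly hazard and near-full retention, and Protocol 6.5 ends treatment for reasons such as no migraine treated before the Week 8 visit and poor diary completion. A reader might also infer that the endpoint is shown by enrollment group alone. It is also tabulated by subgroup, though still as crude percentages.

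**Conclusion.** The gap is real. This primary endpoint has no exposure-adjusted or fixed-time summary, its columns cover unequal planned durations, and the SAP corrects for exposure in comparable tables. At equal weekly risk the crude display favours EOD+PRN unless essentially all such events occur by Week 12.

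The size is conditional. Under constant or front-loaded hazards the distortion lies between 1 and about 4.3, and the documents give nothing that would narrow this. If risk follows tablets instead of weeks, the contrast with PRN (2-8) could vanish or reverse, and that with PRN (9-14) would be below four-fold over most of the range. The point deserves correction before the report. It does not threaten the data or the other primary endpoints.

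**What to change.** In SAP 4.8.2, under on-treatment AEs:

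- Add *Exposure-adjusted AEs leading to study drug discontinuation*, by enrollment group and overall, with the method and reference dates already set for AEs and SAEs.
- Add the cumulative incidence of AE-related discontinuation through Week 12 for all enrollment groups, with confidence intervals. Count time from first dose, treat other-cause discontinuation as a competing event and planned completion as censoring, and state how the 7-day window is handled.

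The hepatic-related version, a secondary endpoint, has the same layout and could be added at the same time.

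The cost is one or two extra tables built on dates the SAP already derives. The exposure-adjustment method is in the Core SAP, which is not among the documents, so the programming effort cannot be confirmed. The EOD+PRN estimates will be imprecise, with 1 or 2 events expected at an assumed 3% 52-week risk, which is why the intervals belong in the table.
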